5.1 Primary Endpoint(s)

Primary Safety Endpoint

Major Adverse Events (MAE) at 30 days defined as:

- Need for emergency surgical revascularization of target limb
- Unplanned target limb major amputation (above the ankle)
- Symptomatic thrombus or distal emboli that require surgical, mechanical or pharmacologic means to improve flow and extend hospitalization
- Perforations that require an intervention, including bail-out stenting

Primary Performance Endpoint(s)

Technical success is defined as final residual stenosis $\leq 30\%$ without flow-limiting dissection (\geq Grade D) of the lesion by angiographic core lab.

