5.2 Secondary Endpoint(s)

Performance

- IVL Technical success is defined as residual stenosis $\leq 30\%$ without flow-limiting dissection (\geq Grade D) of the lesion post-IVL by angiographic core lab.
- Procedural success is defined as final residual stenosis $\leq 30\%$ without any flow-limiting dissection (\geq Grade D) in all target lesions by angiographic core lab.

Safety

- MAE at 6 and 12 months

Patency

- Primary patency at 12 months defined as freedom from clinically-driven target lesion revascularization (TLR) and freedom from restenosis determined by duplex ultrasound or angiogram $\geq 50\%$ stenosis. Acute PTA failure requiring a stent of the target lesion at any time during the index procedure will be counted as a loss of primary patency.
- Clinically driven target lesion revascularization (TLR) at 30 days, 6 and 12 months

Clinical

- Ankle-brachial index (ABI) at 12 months, reported as change from baseline
- Rutherford Category at 30 days, 6 and 12 months, reported as change from baseline

	No.: CP 64007	REV. D
	TITLE: Disrupt PAD+ Study	
	CLASS: CLINICAL PROTOCOL	PAGE 14 OF 57

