9.0 DATA ANALYSIS PLAN

9.1 General Statistical Methods

Descriptive statistics will be provided in this study. Analyses will be conducted at pre-specified time points including 30 days, 6 and 12 months.

Categorical data will be summarized using frequency tables, presenting the subject counts and percentages. McNemar's chi-square may be used to assess within-subject changes in a bivariate response variable.

Continuous variables will be summarized by the mean, standard deviation, median, minimum and maximum. Within-subject changes will be analyzed parametrically using the Paired t-test if the differences are normally distributed, or non-parametrically using the Sign-Rank Test if the differences are not normally distributed.

Exact confidence intervals will be generated for estimates of proportions. Asymptotic confidence intervals will be generated for estimates of means. The p-values of all tests will be reported without any correction for the multiplicity of tests performed.

Statistical analyses will be performed using SAS System® Version 9.4. Analyses will be performed on all subjects enrolled in the study cohort.

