9.2 Sample Size Determination

This study will enroll a minimum of 40 lesions in up to 40 subjects at up to 10 sites in Australia, New Zealand and the US with the aim of treating at least 20 target lesions with the 8.0 mm IVL catheter. A maximum of three target lesions may be treated per subject. The results from this study will provide estimates of the primary and secondary safety and performance endpoints. Two-sided 95% Confidence Intervals will be calculated for each endpoint.

As a confirmatory study, the sample size was justified using methods similar to those that would be used to justify a feasibility study. Sample sizes justifications in research and medical device development vary with four main methodological approaches: rules of thumb, conceptual models, numerical guidelines derived from empirical studies, and statistical formulas (J. Sim, Saunders, Waterfield, & Kingstone, 2018). For feasibility studies, the rule of thumb approach is most often applied, and sample sizes between 12 and 50 have been recommended (Browne, 1995; Hertzog, 2008; Julious, 2005; J. Sim & Lewis, 2012; Stallard, 2012). The sample size for the PAD+ study (n=40) is in keeping with these published recommendations and is therefore justified.

Assuming a primary performance point estimate of 65% for Procedural Success (derived from the PAD III study of peripheral IVL using the M⁵ catheter) (Gray, 2020), a sample size of 40 lesions would result in a 2-sided 95% CI of [48.3,79.4]. The lower bound of this interval is similar

	No.: CP 64007	REV. D
	TITLE: Disrupt PAD+ Study	
	CLASS: CLINICAL PROTOCOL	PAGE 27 OF 57

to the PTA (control) arm of PAD III study (50.4%) (Gray, 2020), which is sufficient given the aims of the research.

These data provide reasonable evidence of safety and performance.

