10.4 Serious and Non-serious Adverse Event Reporting Requirements

10.4.1 AE Reporting Requirements

All AE information will be collected from enrollment through 12 months follow-up.

AEs should be reported in the subject's medical records as applicable and on the Adverse Event Case Report Form (AE CRF). Data reported should include date of onset, treatment, resolution, and an assessment of both seriousness and relationship to the study device and procedure. AEs will be followed until the event has resolved (in the case of permanent impairment, the event will be followed until it stabilizes and the overall clinical outcome has been ascertained).

Any AEs that meet IRB/EC reporting requirements must be reported per the institution's policy.

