15.0 DEFINITIONS and ABBREVIATIONS

15.1 Study Definitions

Access Site Hemorrhage: Bleeding from the access site which requires transfusion, hospitalization (either admission or extended stay), or further treatment for management. Hemorrhage, without frank bleeding, needing ≥ 1 unit RBCs will be considered a serious adverse event.

Access Site Infection: Culture-proven wound infection or presumptive treatment with antibiotics for clinically diagnosed wound infection.

Acute Renal Failure: Acute post-operative renal insufficiency resulting in one or more of the following: (a) increase of >1.0 mg/dl in serum creatinine from most recent prior measured level, and current measured absolute value is >2.0 mg/dl; (b) a new requirement for dialysis.

Adverse Device Effect (ADE): An adverse event related to the use of the medical device. This definition includes any event resulting from insufficiencies or inadequacies in the instructions for use or the deployment of the device. This definition includes any event that is a result of a user error.

Note: This definition includes adverse events resulting from insufficient or inadequate Instructions for Use, deployment, implantation, installation, or operation, or any malfunction of the investigational medical device.

Note: This definition includes any event resulting from insufficiencies or inadequacies in the Instructions for Use, deployment of the device or any event that is a result of user error or intentional abnormal use of the investigational medical device.

Adverse Event (AE): An adverse event (AE) is any untoward medical occurrence, unintended disease or injury, or untoward clinical signs (including abnormal laboratory findings) in subjects, users or other persons, whether or not related to the investigational device/procedure.

Air Embolism: An inadvertent introduction of air or gas to the vasculature that requires medical treatment.

Allergic Reaction: An allergic reaction characterized by rash, nausea, vomiting, upper respiratory congestion, urticaria, shortness-of-breath, vasovagal reaction, or general cardiovascular collapse (anaphylaxis).

Amputation (major): Any requirement for amputation above the ankle or higher.

Amputation (minor): Any requirement for amputation below the ankle.

Amputation, Unplanned: An amputation associated with the target limb that occurs between the index procedure and 30 days that was not previously planned as part of the overall treatment strategy.

	No.: CP 64007	REV. D

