Fever: A temperature 38°C (>101.4° F) not related to a culture positive infection.

General Discomfort: Physical or psychosocial signs or symptoms commonly associated with hospitalization that are investigated and determined to require minor (i.e., aspirin, non-narcotic medication) or no treatment.

Hematoma: Collection of blood (or its degradation products) which exceeds 5 cm in diameter, requires treatment, or prolongs hospitalization.

	No.: CP 64007	REV. D
	TITLE: Disrupt PAD+ Study	
	CLASS: CLINICAL PROTOCOL	PAGE 47 OF 57

Hemorrhage: Any bleeding which results in a drop in hematocrit from pre-procedure level which is associated with hemodynamic compromise or which results in a hematocrit of $\leq 30\%$, or blood loss that requires transfusion.

Hypertension: Systolic BP >140 mmHg, or diastolic >90 mmHg requiring specific medical therapy.

Iliofemoral DVT: Defined as DVT involvement of the common or external iliac veins or the common femoral vein, with or without distal (e.g., toward foot) DVT involvement, based on duplex ultrasound exam.

Infection, access site: Infection at the vascular access site, documented by lab culture or clinical evidence requiring medical treatment (irrigation, debridement, antibiotics, etc.) to resolve.

Infection, sepsis: Culture-proven infections or presumptive treatment with antibiotics for clinically diagnosed infection.

Infection, systemic: Systemic infection documented by positive lab culture or clinical evidence, requiring medical treatment to treat and resolve.

Intracranial Hemorrhage: Includes all bleeding within the cranium either subarachnoid, intraparenchymal, or intracerebral.

Intravascular Lithotripsy (IVL), formerly known as Intravascular Lithoplasty: Shockwave Medical's proprietary balloon angioplasty catheter including lithotripsy technology that creates pulsatile mechanical energy for disrupting calcified vascular plaque.

Limb Ischemia: Deficient supply of oxygenated blood to the tissues in the limbs that is due to obstruction of the inflow of arterial blood characterized by pain and/or discoloration of the limb.

Lithotripsy: A medical procedure for disrupting calculus in the body.

Luminal Patency: Post-procedure residual stenosis $<50\%$ as determined by investigator visual assessment or quantitative analysis of the end of procedure angiogram.

Major Adverse Event (MAE): For the purposes of this study, the definition of Major Adverse Event(s) includes:

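### Unplanned amputation is defined to end at 30 days, so the amputation component of MAE at 6 and 12 months cannot rise above its 30-day count

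*Combined protocol and SAP*

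**What the plan says.** Four parts of the protocol bear on this point.

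- **Endpoint.** The amputation item of the MAE composite in Section 5.1 reads "Unplanned target limb major amputation (above the ankle" (closing bracket cut). The Study Summary (Section 2.0) and the MAE entry in Section 15.1 repeat it. The latter is introduced by "For the purposes of this study, the definition of Major Adverse Event(s) includes".
- **Time points.** The 30-day MAE rate is the primary safety endpoint. Section 5.2 adds "MAE at 6 and 12 months", the only item under its Safety heading, and gives no separate definition for the later time points.
- **Glossary.** Section 15.1 defines an unplanned amputation as "An amputation associated with the target limb that occurs between the index procedure and 30 days" that was not planned beforehand as part of the treatment strategy. A major amputation is "Any requirement for amputation above the ankle or higher", with no time limit.
- **Data collection.** Section 10.4.1 states: "All AE information will be collected from enrollment through 12 months follow-up".

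**The concern.** The 30-day limit is part of the definition of the term the composite uses. It suits the primary endpoint, but the same term carries into the 6- and 12-month endpoint, where it switches the amputation component off after the first month.

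Major amputation is an outcome that long follow-up ought to catch in this population. Eligibility extends to Rutherford categories 4 and 5 (rest pain and minor tissue loss), and Section 3.1 names amputation as a consequence of the disease. A late amputation would be collected as an adverse event but left out of the reported MAE rate, unless the same subject had another MAE component. In a study of at most 40 subjects, one event decides whether the 12-month report shows no MAE or an MAE.

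**Working it through.** **1. The text.** To count as an MAE, an amputation must be (a) of the target limb, (b) major and (c) unplanned. Condition (c) has two parts under Section 15.1: it was not previously planned, and it fell between the index procedure and day 30.

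| Event | Target limb | Major | Not planned | By day 30 | MAE as written |
|---|---|---|---|---|---|
| Unplanned above-ankle amputation, day 20 | yes | yes | yes | yes | yes |
| Same event, day 31 | yes | yes | yes | no | no |
| Same event, day 300 | yes | yes | yes | no | no |

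Nothing in Sections 2.0, 5.2, 9 or 15.1 replaces the window for the later time points. The amputation count at 6 and 12 months therefore equals the 30-day count.

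**2. Follow-up time left out of this component.**

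- 12 months: (365 − 30)/365 = 335/365 = 92% of days.
- 6 months, taken as 182 days: (182 − 30)/182 = 152/182 = 84% of days.

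These are shares of calendar time, not of events.

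**3. The interval method.** Section 9.1 states: "Exact confidence intervals will be generated for estimates of proportions". The Clopper-Pearson limits for x events in n are Beta(0.025; x, n − x + 1) and Beta(0.975; x + 1, n − x). The plan's only computed interval is in Section 9.2: 65% of 40 lesions, which is 0.65 × 40 = 26/40. The formula gives 48.3% to 79.4%, as printed there, so the same method is used below.

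**4. Illustration.** Assume one unplanned target-limb major amputation after day 30 in a subject with no other MAE, no MAE in anyone else, and every subject evaluable.

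| Subjects | If the late event counts | As reported under Section 15.1 |
|---|---|---|
| 40 | 1/40 = 2.5% (0.1 to 13.2%) | 0/40 (0 to 8.8%) |
| 14 | 1/14 = 7.1% (0.2 to 33.9%) | 0/14 (0 to 23.2%) |

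Forty is the maximum number of subjects. Fourteen is the smallest number that can supply 40 lesions, because "A maximum of three target lesions may be treated per subject": 40/3 = 13.3, rounded up to 14. Section 9.4 allows no imputation, so the actual denominator may be smaller than the number enrolled.

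**5. How likely is a missed event?** The documents give no rate, so take a range for the risk p of such an amputation between day 31 and month 12. With 40 subjects, the expected number is 40p and the chance of at least one is 1 − (1 − p)^40.

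| Assumed p | Expected uncounted events | Chance of at least one |
|---|---|---|
| 1% | 0.4 | 33% |
| 2% | 0.8 | 55% |
| 5% | 2.0 | 87% |

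Under the current definition the component adds none of these after day 30, whatever p is.

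**The case against.** The best reply is that the limit is wording left over from the primary endpoint and nobody would apply it. The MAE entry itself has no time limit, Section 5.2 plainly asks for later rates, and Section 13.1 gives the CEC the task of setting event criteria in a charter that is not among these documents. That charter may already use a longer window. This stands as a statement about practice: how late amputations would actually be classified is unknown. It does not rescue the text, since a charter that counted them would contradict Section 15.1, and the rate would depend on which document the adjudicators followed. Nor does the word 'includes' in the MAE entry help, because Sections 2.0 and 5.1 define MAE by the same four items.

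Second, the consequence is limited. The analysis is descriptive with no safety threshold, so no decision rule changes. A late major amputation would normally be a serious adverse event under Section 10.1.2, reportable within 48 hours under Section 10.4.2. Both points are right: the event is not lost. The MAE rate would still be wrong.

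Third, the 14-subject case is extreme. With a maximum of 42 lesions, at least 12 of the 14 subjects would need three each. That is fair, and the 40-subject row is the better guide.

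Fourth, the other components may add little after day 30 either, since perforation is largely a procedural event. If so, the late MAE rate leans more heavily on amputation and emergency surgery, which makes the gap matter more.

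**Conclusion.** The concern holds. As written, the protocol sets a rule that gives too low a 6- and 12-month MAE count whenever an unplanned target-limb major amputation after day 30 occurs in a subject with no other MAE component. Each such subject lowers the reported rate by 2.5 percentage points with 40 evaluable subjects, and by 7.1 points in the 14-subject extreme. Whether any will occur cannot be judged from the documents, and the rates tried above are assumptions. The conclusion rests on reading the glossary term literally and on no other rule applying through the unseen CEC charter. It is limited to one component of a secondary endpoint. It should be fixed, because this is the only secondary safety endpoint and the correction is simple.

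**What to change.** In Section 15.1, define an unplanned amputation as a target-limb amputation that was not previously planned as part of the overall treatment strategy and that occurs from the index procedure through the time point being reported (30 days, 6 months or 12 months). Leave the MAE item as it is and use the same definition in the CEC charter.

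The cost is one edit to the protocol and one to the charter, submitted to the IRB/EC under Section 11.6, plus re-review of any amputation after day 30 already adjudicated. Adverse events are already collected through 12 months. The data items listed in Section 10.4.1 do not include whether an amputation had been planned, so check that the case report form or source documents supply this for late events, as they must for the 30-day endpoint. The reported 6- and 12-month rates may come out slightly higher.

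As a separate clarification, not an error, the same amendment could say whether the extended-hospitalization condition in the thrombus and emboli component includes readmission.

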7.2 Subject Selection

7.2.1 Inclusion Criteria

General Inclusion Criteria

1. Subject is able and willing to comply with all assessments in the study.
2. Subject or subject's legal representative have been informed of the nature of the study, agrees to participate and has signed the approved consent form.
3. Age of subject is > 18.
4. Rutherford Clinical Category 2, 3, 4 or 5 of the target limb(s).
5. Estimated life expectancy >1 year.
6. Subject is intended to undergo treatment with Shockwave M⁵⁺Peripheral IVL System for de novo lesions of the ilio-femoropopliteal arteries.

Angiographic Inclusion Criteria

7. Single or multiple de novo target lesion(s) located from the common iliac to the femoropopliteal artery, in one or both limbs.
8. Target lesion reference vessel diameter is between 3.5mm and 10.0mm by visual estimate.
9. Target lesion is ≥70% stenosis by investigator via visual estimate.
10. Target lesion length is ≤200mm for lesions 70-99% stenosed. Target lesion can be all or part of the 200mm treated zone.

	No.: CP 64007	REV. D
	TITLE: Disrupt PAD+ Study	
	CLASS: CLINICAL PROTOCOL	PAGE 16 OF 57

11. Chronic total occlusion, lesion length is ≤ 100 mm of the total ≤ 200 mm target lesion.
12. Subject has at least one patent tibial vessel on the target leg with runoff to the foot, defined as no stenosis $> 50\%$.
13. Calcification is at least moderate defined as presence of fluoroscopic evidence of calcification: 1) on parallel sides of the vessel and 2) extending $> 50\%$ the length of the lesion if lesion is ≥ 50 mm in length; or extending for minimum of 20mm if lesion is < 50 mm in length.

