Closure, Subacute: Target lesion site occlusion that occurs after the index procedure is completed (e.g., the subject has left the treatment area) and within 30 days of procedure.

Congestive Heart Failure: Documentation of one of the following: a) paroxysmal nocturnal dyspnea (PND), b) dyspnea on exertion (DOE) due to heart failure, or c) elevated pulmonary capillary wedge pressure (PCWP) with associated shortness of breath (SOB) or x-ray consistent with congestion. May be related to fluid overload in the presence of underlying cardiovascular disease.

	No.: CP 64007	REV. D
	TITLE: Disrupt PAD+ Study	
	CLASS: CLINICAL PROTOCOL	PAGE 45 OF 57

Contrast-Induced Nephropathy: Associated with contrast agent resulting in >25% increase in serum creatinine or an absolute value of >0.5 mg/dl.

Contrast Media Reaction: An allergic reaction, immediate or delayed, associated with the intravascular administration of contrast media that results in symptoms (e.g., itching, hives) or physiologic changes requiring treatment (e.g., anaphylactic reaction) or death.

Critical Limb Ischemia: Clinical manifestation of peripheral arterial disease characterized by Rutherford Clinical Scale Category of 2-6. (For the purposes of this study, only subjects with Rutherford Clinical Scale Category of 2, 3, 4, and 5 are eligible for enrollment).

Death: (divided into 2 categories)

Cardiac death is death due to any of the following:

1. Acute myocardial infarction
2. Cardiac perforation/pericardial tamponade
3. Arrhythmia or conduction abnormality
4. Stroke within 30 days of the procedure or stroke suspected of being related to the procedure
5. Death due to complication of the procedure, including bleeding, vascular repair, transfusion reaction, or bypass surgery
6. Any death for which a cardiac cause cannot be excluded

Non-cardiac death is a death not due to cardiac causes (as defined immediately above).

De novo: A segment of artery that has not previously been treated with angioplasty or stenting.

Deep Vein Thrombosis (DVT): Thrombosis of a deep vein, as confirmed by imaging study or direct visualization.

Device Deficiency: is an inadequacy of a medical device with respect to its identity, quality, durability, reliability, safety or performance (includes malfunctions, use errors, and inadequate labeling).

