Rutherford Clinical Category Scale: Clinical scale identifying three grades of claudication and three grades of critical limb ischemia ranging from rest pain alone to minor and major tissue loss. (ACC/AHA PAD Practice Guidelines – Hirsch et al. 2005)

	No.: CP 64007	REV. D
	TITLE: Disrupt PAD+ Study	
	CLASS: CLINICAL PROTOCOL	PAGE 49 OF 57

Grade	Category	Clinical Description
	0	Asymptomatic
I	1	Mild claudication
	2	Moderate claudication
	3	Severe claudication
II	4	Ischemic rest pain
	5	Minor tissue loss
III	6	Ulceration or gangrene

Septicemia: One positive blood culture AND clinical evidence for infection (e.g., fever, elevated WBC count, hypotension, need for increased inotropic support, end organ dysfunction, coagulopathy/ DIC [disseminated intravascular coagulation], need for increased ventilator support, etc.).

Serious Adverse Device Effect (SADE): A serious adverse device effect is defined as an adverse device effect that results in any of the consequences characteristic of a serious adverse event or that might have led to any of these consequences if suitable action had not been taken, intervention had not been made, or if circumstances had been less opportune.

Serious Adverse Event (SAE): A serious adverse event (SAE) is defined an adverse event that:

- led to death,
- led to a serious deterioration in the health of the subject, that either resulted in:
 - a life-threatening illness or injury, or
 - resulted in a permanent impairment of a body structure or a body function, or
 - required in-patient hospitalization or prolongation of existing hospitalization, or
 - resulted in medical or surgical intervention to prevent life-threatening illness or injury or permanent impairment to body structure or a body function, or,
 - led to fetal distress, fetal death or a congenital abnormality or birth defect.

Note: Planned hospitalization for a pre-existing condition, or a procedure required by the investigational plan without serious deterioration in health, is not considered a serious adverse event.

Stroke: any neurological deficit lasting 24 hours or longer, or lasting less than 24 hours with a brain imaging study showing infarction consistent with deficit. May be further categorized as:

- Ischemic Stroke: neurologic deficit meeting the study definition for Stroke that is attributed to thromboembolic event.

	No.: CP 64007	REV. D
	TITLE: Disrupt PAD+ Study	
	CLASS: CLINICAL PROTOCOL	PAGE 50 OF 57

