- Hemorrhagic Stroke: neurologic deficit meeting the study definition for Stroke that is attributed to bleeding into brain tissue, epidural, subdural, or subarachnoid space; or a combination of these sites.

Target Lesion Revascularization, Clinically-driven (TLR):

A target lesion revascularization performed due to target lesion diameter stenosis $\geq 50\%$ and either evidence of clinical or functional ischemia (e.g., recurrent/progressive life-limiting intermittent claudication, claudication unresponsive to medical therapy, CLI) or recurrence of the clinical syndrome for which the initial procedure was performed. Clinically driven target lesion revascularization occurs in the absence of protocol directed surveillance ultrasound or angiography.

Target Vessel Revascularization, Clinically-driven (TVR), non-TLR: A target vessel revascularization performed due to non-target lesion diameter stenosis $\geq 50\%$ and either evidence of clinical or functional ischemia (e.g., recurrent/progressive life-limiting intermittent claudication, claudication unresponsive to medical therapy, CLI) or recurrence of the clinical syndrome for which the initial procedure was performed. Clinically driven target vessel revascularization occurs in the absence of protocol directed surveillance ultrasound or angiography.

Total Occlusion A 100% stenotic lesion as documented by angiographic absence of flow.

Thrombocytopenia: A persistent decrease in the number of blood platelets to subnormal levels.

Thrombus: Blood clot that obstructs a blood vessel.

Transient Ischemic Attack (TIA): Focal neurologic abnormalities of sudden onset and brief duration (i.e., lasting less than 24 hours and, if an imaging study is performed, shows no evidence of infarction).

Toe / Brachial Index (TBI): The ratio of systolic blood pressure measured at the toe to systolic blood pressure measured at the brachial artery.

Unanticipated Adverse Device Effect (UADE): An Unanticipated Adverse Device Effect (UADE) is defined as any serious adverse effect on health or safety or any life-threatening problem or death caused by or associated with the device, if that adverse effect, problem, or death was not previously identified in nature, severity, or degree of incidence in the protocol or application (including a supplementary plan or application), or any other unanticipated serious problem associated with a device that relates to the rights, safety, or welfare of subjects.

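### Critical limb ischemia is defined as Rutherford 2-6, against the study's own scale, which loosens the clinical test in the secondary endpoint of clinically-driven TLR

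*Combined protocol and SAP*

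**What the plan says.** All the relevant wording is in section 15.1 (Study Definitions).

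- **Critical Limb Ischemia.** The entry describes disease "characterized by Rutherford Clinical Scale Category of 2-6" and adds in parentheses that only categories 2 to 5 may enrol.
- **Rutherford Clinical Category Scale.** The entry describes "three grades of claudication and three grades of critical limb ischemia ranging from rest pain alone". In its table category 2 is "Moderate claudication", category 3 is severe claudication and category 4 is ischemic rest pain.
- **Target Lesion Revascularization, Clinically-driven.** The revascularization must be for a target lesion stenosis of at least 50%. In addition there must be clinical or functional ischemia, with the examples "recurrent/progressive life-limiting intermittent claudication, claudication unresponsive to medical therapy, CLI", or else "recurrence of the clinical syndrome for which the initial procedure was performed". It must also arise in the absence of protocol-directed surveillance imaging. The entry for clinically-driven target vessel revascularization (TVR, non-TLR) uses the same ischemia examples.

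Section 5.2 makes clinically-driven TLR at 30 days, 6 and 12 months a secondary endpoint. It also makes freedom from clinically-driven TLR one component of 12-month primary patency; the other is freedom from restenosis of at least 50% by duplex or angiogram. Section 15.2 has no entry for the abbreviation CLI, so the Critical Limb Ischemia entry is the only definition supplied.

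**The concern.** The TLR definition qualifies the kind of claudication it gives as an example: life-limiting and recurrent or progressive, or not responding to medical therapy. CLI carries no such qualifier. If CLI begins at Rutherford 2, moderate or severe claudication meets the CLI example directly, and the qualifiers on claudication do no work in categories 2 and 3.

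Inclusion criterion 4 in section 7.2.1 admits Rutherford 2 to 5, so every eligible subject counts as CLI at baseline. A subject treated at category 4 or 5 who improves to category 2 or 3 still counts as CLI at a later revascularization.

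At stake is whether clinically-driven TLR measures what its name says. The parenthesis on enrolment suggests that the eligibility range found its way into the disease definition. That is an inference; the contradiction does not depend on it.

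**Working it through.** **1. The plan's own figure.** The plan computes nothing for TLR. Its only computed interval is in section 9.2: 65% with 40 lesions, 95% CI [48.3, 79.4]. The exact (Clopper-Pearson) interval for 26/40 is [48.32, 79.37], which matches; a Wald interval would be [50.2, 79.8]. This figure does not involve CLI. It confirms that the exact method promised in section 9.1 is the one to use in step 5.

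**2. The two entries side by side.**

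| Rutherford category | Scale entry | CLI entry |
|---|---|---|
| 1 | claudication | not CLI |
| 2 | claudication | CLI |
| 3 | claudication | CLI |
| 4, 5, 6 | CLI | CLI |

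They disagree on categories 2 and 3.

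**3. Effect on the TLR rule.** Treat the examples in the rule as a closed list, the reading most favourable to the concern, and write:

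clinically-driven TLR = (stenosis ≥50%) AND (limiting or refractory claudication OR CLI OR recurrence of the presenting syndrome) AND (no surveillance trigger).

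Enumerate the logical cases:

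- stenosis ≥50%: yes or no, 2 values;
- baseline Rutherford 2 to 5: 4 values;
- current symptom state: 10 values. Categories 0, 4, 5 and 6 give one state each. Categories 1, 2 and 3 give two each, with or without limiting or refractory claudication: 4 + 3 × 2 = 10;
- recurrence: 2 values; surveillance trigger: 2 values.

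Total: 2 × 4 × 10 × 2 × 2 = 320 combinations. These are logical cases, not expected frequencies.

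Classify each with CLI = 2-6 and with CLI = 4-6. The result differs only when stenosis is ≥50%, current category is 2 or 3, claudication is neither limiting nor refractory, there is no recurrence and there is no surveillance trigger. That is 4 baseline categories × 2 current categories = 8 of 320. In all 8 the case is an event under 2-6 and not under 4-6, so the change goes one way. The rule still rejects 248 of 320 under 2-6, against 256 under 4-6.

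**4. Effect on primary patency.** Patency is lost on clinically-driven TLR or on restenosis ≥50%, the latter with no symptom condition. Every clinically-driven TLR already requires stenosis ≥50%, and section 7.8.5 sends the revascularization angiogram to the core lab. The set of subjects who lose patency is therefore the same under either CLI range: 0 of 320 combinations change.

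**5. Size on the TLR rate.** One event in a denominator of 40 is 1/40 = 2.5 points. The documents give no rate of revascularization for non-limiting claudication, so the number of added events k is an assumption:

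| k | Points added (k/40) |
|---|---|
| 0 | 0 |
| 1 | 2.5 |
| 2 | 5.0 |
| 3 | 7.5 |
| 4 | 10.0 |

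For scale, the exact 95% interval is [0.6, 16.9] for 2/40 = 5.0%, [1.6, 20.4] for 3/40 = 7.5% and [2.8, 23.7] for 4/40 = 10.0%. A shift of one or two events lies well inside the sampling uncertainty.

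**The case against.** The strongest reply is that CLI is only one item in a list of examples. The operative test is evidence of clinical or functional ischemia, and section 15.1 defines limb ischemia broadly, by pain or discoloration from obstructed inflow. A symptomatic subject at Rutherford 2 or 3 with a stenosis of at least 50% might then qualify without the word CLI. This stands in part: the more open the list, the less the CLI wording adds. But a case that fits a listed example plainly satisfies the rule, so the definition of that example still matters.

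Second, for a subject treated at Rutherford 2 or 3, returning claudication already qualifies as recurrence. That stands, and it narrows the affected group to persisting or mild claudication without recurrence, or a subject treated at category 4 or 5 who now has only claudication.

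Third, under section 13.1 the Clinical Events Committee develops its own endpoint criteria in a charter. That stands as a limit on what can be said. The charter is not supplied, and the protocol does not say whether TLR is adjudicated. A reader might infer that the committee would apply the 2-6 range; the documents do not show this. Equally, nothing supplied overrides it.

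A reader might also infer that the clinical filter on TLR fails altogether, or that primary patency is distorted. Neither is supported. The stenosis and surveillance conditions still operate, as does the exclusion of categories 0 and 1 without a qualifying symptom or recurrence. Patency already turns on a stenosis threshold that every clinically-driven TLR must meet.

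**Conclusion.** The contradiction is certain from the text, and it reaches one named secondary endpoint. Under the written definition clinically-driven TLR is loosened for one group: Rutherford 2 or 3 at revascularization, stenosis of at least 50%, claudication neither life-limiting or progressive nor refractory, no recurrence of the presenting syndrome, and no surveillance trigger. Events can only be added, at 2.5 points each with a denominator of 40, and by less or more if the evaluable number is larger or smaller. How many such events would occur is unknown.

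The conclusion assumes that the written definition is applied and that the listed examples decide the ischemia test. Clinically-driven TVR shares the wording but is not a listed endpoint. No primary endpoint, eligibility criterion or sample-size figure uses the CLI definition.

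A reader might go further and say that the wording spoils comparison with the 8.6% TLR rate in section 3.1. The documents do not support that. No such comparison is planned and the analysis is descriptive. The 8.6% was obtained without drug-coated balloons or drug-eluting stents, whereas section 7.7.2 allows both here, and the earlier study's TLR definition is not given. The intervals for 2/40 and 4/40 both contain 8.6%.

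This is worth correcting because it affects an endpoint definition and is cheap to correct, not because a large bias has been shown.

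**What to change.** In section 15.1, reconcile the Critical Limb Ischemia entry with the Rutherford scale entry by defining CLI as the three critical-limb-ischemia categories of that scale (4-6). Move the remark on enrolment of categories 2 to 5 out of the definition and leave it to the eligibility criteria. Add CLI to the abbreviation list in section 15.2. Use the same definition for classifying clinically-driven TLR and TVR, including in the Clinical Events Committee charter if the committee adjudicates them.

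The cost is one definition line, plus the abbreviation entry and, where relevant, the matching charter line. No new data are needed: Rutherford category is already recorded at baseline, at each follow-up visit from 30 days, and before any target limb revascularization (sections 7.4 and 7.8.5). After the change the reported clinically-driven TLR rate could only stay the same or fall, so the change should be made and dated before TLR events are classified.
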